## 9.2 Packaging and Storage

## 9.2.2 Packaging

Study drug labels will be developed in accordance with cGMP and local regulatory requirements.

## 9.2.3 Storage Conditions

Confidential

Temperature excursions outside of the defined ranges should be reported to the Sponsor, the product should be immediately quarantined and only used if/after Sponsor approval has been obtained. For further details please refer to the Pharmacy Manual.

## 9.2.4 Drug Substance Shipment

Drug substance will be shipped under monitored temperature conditions. Refer to the Pharmacy Manual for receipt instructions.

### 9.3 Drug Administration

The study drug should be dispensed under the supervision of the Investigator or a suitably qualified member of the study team. The Investigator or designee agrees to store and dispense the study drug per this protocol.

For Part I, there are up to 9 planned cohorts in this study. A sentinel group of 2 subjects will be randomized to active or placebo (1:1 active and placebo) and will be dosed ahead of remaining subjects of each cohort (Section 9.1.3).

For Part I, study drug will be administered under fasting condition

Subject will

fast for at least 10 hrs prior to receiving study drug

Dosages provided in capsules should be swallowed whole. Subjects must avoid poppy seeds, grapefruit and grapefruit juice while on study drug. Subjects should be advised to avoid food and liquids other than water for at least 2 hours prior to dosing until at least 1 hour after dosing.

See Table 2 for summary of dose per cohort.

Cohort		1	2	3	4	5
	Active N=6	INDV-2000, 1 mg	INDV-2000, 5 mg	INDV-2000, 20 mg	INDV-2000, 50 mg	INDV-2000, 120 mg
Dose	Placebo N=2	INDV-2000 Placebo,1 mg	INDV-2000 Placebo, 5 mg	INDV-2000 Placebo, 20 mg	INDV-2000 Placebo, 50 mg	INDV-2000 Placebo, 120mg
Dosage Form (Active; Placebo)						

#### Table 2 Part 1 Single Ascending Dose IMP Dosing

Cohort		6	7	8	9
	Active	INDV-2000,	INDV-2000,	INDV-2000,	INDV-2000,
	N=6	Dose 6	Dose 7	Dose 8	Dose 9
Dose	Placebo	Placebo, to	Placebo, to	Placebo, to	Placebo, to
	N=2	match	match	match	match
Dosage Form (Active; Placebo)					

Safety and PK evaluation at each dose level. Sentinel dosing at all dose levels.

Part II of the study is a cross-over, food interaction evaluation where INDV-2000 will be given once under fasting conditions and once at completion of a standard FDA High-Fat Breakfast.

There will be 2 treatment arms of 8 subjects each, fed and fasted, with the same treatment order randomly assigned within subject. The same INDV-2000 dose will be used for fed and fasted conditions. Dose level is to be determined following Part 1.

For the fasting condition of Part II, subjects will receive INDV-2000 following an overnight fast of at least 10 hrs. Subjects will be administered INDV-2000 with 240 mL (8 ounces) of water.

No food will be allowed for at least 4 hours post-dose administration. Water is allowed as desired except for at least 1 hour before and at least 1 hour after drug administration.

For the food effect evaluation of Part II, subjects will consume a high-fat meal within 30 minutes prior to INDV-2000 administration. The high-fat meal should provide approximately 800 to 1000 calories, and should derive approximately 150, 250 and 500 to 600 calories from protein, carbohydrate and fat, respectively. Examples of an appropriate high-fat meal are provided in Secition 22.5, Appendix 5. Subjects should consume the entire meal in 30 minutes or less; however, the dose must be administered 30 minutes after the start of the meal. If the subject cannot complete the meal, the approximate percentage of the meal consumed should be recorded in the eCRF and continue with the study. Additionally, the start and finish time of the meal will be recorded in the eCRF. INDV-2000 will be administered with 240 mL (8 ounces) of water. No food will be allowed for at least 4 hours post-dose administration. Water is allowed as desired except for at least 1 hour before and at least 1 hour after drug administration.

Lunch will be provided at least 4 hr post- INDV-2000 (or - placebo) dose for both parts.

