### Part I and Part II (both periods, fasting and fed)

The following criteria must be met at Day -1 for the subject to be enrolled in the study.

- 1. Female subjects must have a negative urine pregnancy test.
- 2. Subjects must not have a Corrected QT value (QTcF) >450 msec for males and >470 msec for females.
- 3. Subjects must have a negative result obtained from the urine drug screen (UDS) and the alcohol test (urine ethanol).
  - a. Subjects who have a positive result for alcohol will be asked to refrain from alcohol and return the next day for retest. This may only occur once.

If any of these criteria are not met, the subject will not be enrolled and randomized in Part 1, or will not be enrolled in Part II, Period 1 – Dosing Under Fasting Conditions, or will not be allowed to move forward into Part II – Dosing after High-Fat Content Meal.

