## 14.4 Key End Point Analyses

#### 14.4.1 Primary Endpoint

The primary endpoint for the study is the incidence, seriousness, severity, and relationship to IMP of TEAEs in the Safety Population.

For Part I of the study, a TEAE is defined as an AE with start date/time at or after IMP dosing. For Part II of the study (a cross-over design), a Period 1 (Fasted) TEAE is defined as an AE with start date/time at or after IMP dosing in Period 1 and no later than IMP dosing in Period 2, and a Period 2 (Fed) TEAE is defined as an AE with start date/time at or after IMP dosing in Period 2 and within the period of time equal to the interval from Period 1 dosing to Period 2 dosing.

The number and percentage of subjects reporting TEAEs will be presented overall, by MedDRA system organ class (SOC) and preferred term (PT), each in descending order of frequency (then alphabetically in case of ties).

IMP-related TEAEs, treatment-emergent SAEs (TESAEs), IMP-related TESAEs, TEAEs leading to death, TEAEs leading to IMP discontinuation, and TEAEs leading to IMP interruption will be presented both overall and by SOC and PT. TEAEs will also be summarized by intensity within SOC and PT. In addition, TEAEs leading to death and IMP-related TEAEs leading to death will be summarized separately by PT.

In summaries by severity and relationship to IMP, if more than one TEAE is coded to the same PT for the same subject, the subject will be counted only once for that PT using the most severe and most related occurrence. Missing severity will be summarized as "severe" and missing relatedness will be summarized as "related."

Separate listings will be presented for TEAEs, TESAEs, TEAEs leading to IMP discontinuation and TEAEs leading to death.

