# 22.5 APPENDIX 5- Example of High-Fat Meal

The following is an example of an appropriate high-fat meal to be consumed within 30 minutes of INDV-2000 administration in Part II, Period 2 on Day 1 for subjects participating in the food effect evaluation.

Food item a	Calories	Fat	Carbohydrates	Protein
	(kcal)	(g)	(g)	(g)
2 eggs, fried	185	14. 1	1.3	12.5
2 strips bacon, fried	84	6.4	0.2	6.0
2 slices of white bread, toasted	129	1.8	24. 0	4.0
4 ounces of hash brown potatoes	207			
8 fluid ounces of whole milk	146			
1 tablespoon butter	102			
Total grams (g)	-			
Total Calories (kcal)	853			
% of Total Calories	100			

a Substitutions can be made as long as the meal provides a similar amount of calories from protein, carbohydrate and fat and has comparable meal volume and viscosity.

22.6 APPENDIX 6- Toxicity Grading Scale for Healthy Adult and Adolescent Volunteers Enrolled in Preventive Vaccine Clinical Trials

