3.2 Treatments

The following treatment will be administered.

Part I: IMP will be administered under fasting condition. Subject will fast for at least 10 hrs prior to receiving the IMP. Subjects should be advised to avoid food and liquids other than water for at least 2 hours prior to dosing until at least 1 hour after dosing. Dose per cohort is detailed in Table 2.

Cohort		1	2	3	4	5
Dose	Active	INDV-2000,	INDV-2000,	INDV-2000,	INDV-2000,	INDV-2000,
	N=6	1 mg	5 mg	20 mg	50 mg	120 mg
Dose	Placebo	INDV-2000	INDV-2000	INDV-2000	INDV-2000	INDV-2000
	N=2	Placebo, 1 mg	Placebo, 5 mg	Placebo, 20 mg	Placebo, 50 mg	Placebo, 120mg
Dosage Form (Active; Placebo)						

Cohort		6	7	8	9
	Active	INDV-2000,	INDV-2000,	INDV-2000,	INDV-2000,
	N=6	Dose 6	Dose 7	Dose 8	Dose 9
Dose	Placebo	Placebo, to	Placebo, to	Placebo, to	Placebo, to
	N=2	match	match	match	match
Dosage Form (Active; Placebo)					

Part II: IMP will be administered under fasting conditions in Period 1 and at completion of a standard FDA high-fat breakfast in Period 2. The same INDV-2000 dose will be used for fed and fasted conditions. Dose level is to be determined following Part I.

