6.6 Standard High Fat Breakfast

Standard high fat breakfast applies only to Part II, Period 2 of the study. Subjects should consume the entire meal in 30 minutes or less, however, the dose must be administered no later than 30 minutes after the start of the meal. Data collected will include meal type, date, time, percent of meal consumed and comment if meal not provided.

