9.1.1 Subject Disposition

A subject disposition summary will show number of subjects screened, number and percentage of screened subjects randomized (Part I) or enrolled (Part II), number and percentage of randomized (Part I) or enrolled (Part II) subjects who discontinued the study, and reasons for discontinuation with number of discontinued subjects as the denominator. Number and percentage of randomized (Part I) or enrolled (Part II) subjects in each analysis population will also be summarized.

Listings of subject disposition and subjects included in each analysis population will be provided. A listing showing that each randomized (Part I) and enrolled (Part II) subject met all inclusion/exclusion criteria will be provided. Reasons for screen failure will also be listed and summarized.

9.1.2 **Protocol Deviations**

Protocol deviations and PK sampling time deviations will be provided in separate listings. Protocol deviation listings will include the deviation description, category, and important/not important designation.

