9.1.9 Adverse event

For Part I of the study, a TEAE is defined as an AE with start date/time at or after IMP dosing.

For Part II of the study (a cross-over design):

A Period 1 (Fasted) TEAE is defined as an AE with start date/time at or after IMP dosing in Period 1 and no later than IMP dosing in Period 2.

A Period 2 (Fed) TEAE is defined as an AE with start date/time at or after IMP dosing in Period 2 and within the period of time equal to the interval from Period 1 dosing to Period 2 dosing.

The number and percentage of subjects reporting TEAEs and number of TEAEs will be presented both overall and by MedDRA SOC and PT, each in descending order of frequency (then alphabetically in case of ties). Separate summaries will be done for IMP-related TEAEs, treatment-emergent SAEs (TESAEs), and IMP-related TESAEs. TEAEs will also be summarized by maximum severity and by maximum toxicity grade within SOC and PT (refer to APPENDIX 3 – Tables for Laboratory Abnormalities for events with toxicity grades determined by the protocol); i.e., if more than one TEAE is coded to the same PT for the same subject, the subject will be counted only once for that PT using the most severe event for the summary by maximum severity, and using the most toxic event for the summary by maximum toxicity.

An overall summary table of TEAEs will be provided that shows incidence and number of events for each of the following:

- Any TEAE
- IMP-related TEAE
- TESAE
- IMP-related TESAE
- Severe TEAE
- TEAE with grade 3 or higher toxicity
- TEAE with outcome of study discontinuation
- Fatal TEAE

If any component of an AE starts date/time is missing such that it cannot be determined whether or not the AE was treatment-emergent, it will be counted in summaries as treatment-emergent. In summaries by relationship to IMP and severity, missing relationship will be summarized as "related" and missing severity will be summarized as "severe."

Protocol No. INDV-2000-101

Separate listings will be presented for TEAEs, TESAEs, TEAEs with outcome of study discontinuation, fatal TEAEs, and non-TEAEs.

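### Part II order is randomly assigned in Protocol 9.3 but fixed as fasted then fed wherever else an order is stated; under the fixed order the food effect is confounded with period

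*Protocol*

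**What the plan says.** Protocol 9.3, on Part II: "There will be 2 treatment arms of 8 subjects each, fed and fasted, with the same treatment order randomly assigned within subject". The sentence is unclear in itself, since one common order and a randomly assigned order do not go together.

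The other places that state an order all give fasted, then fed:

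- SAP 3.2: "IMP will be administered under fasting conditions in Period 1 and at completion of a standard FDA high-fat breakfast in Period 2".
- SAP 6.6: "Standard high fat breakfast applies only to Part II, Period 2 of the study". Protocol Appendix 5 likewise places the meal at "administration in Part II, Period 2 on Day 1 for subjects participating in the food effect evaluation".
- Protocol 14.4.1: "a Period 1 (Fasted) TEAE is defined as an AE with start date/time at or after IMP dosing in Period 1". SAP 9.1.9: "A Period 2 (Fed) TEAE is defined as an AE with start date/time at or after IMP dosing in Period 2".
- Protocol 5.4 attaches the fasting condition to Period 1. The PK sampling table in Protocol Appendix 4 and the Part II schedules in both documents have one fasted Period 1 and one fed Period 2, with no alternative sequence.

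The documents also describe entry to the two parts differently. The Part I schedule has a randomization row and the Part II schedule has none. Protocol 5.4 says that if a check-in criterion fails, "the subject will not be enrolled and randomized in Part 1, or will not be enrolled in Part II, Period 1". SAP 9.1.1 counts the "number and percentage of screened subjects randomized (Part I) or enrolled (Part II").

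The synopsis and Protocol 4.1 say only that each man is dosed once in each condition, so they do not settle the order. SAP section 11 does not mention it.

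**The concern.** The effect of a high-fat meal on absorption and exposure is a stated secondary objective (Protocol 2.2) and the purpose of Part II. A crossover separates treatment from period only if the order varies between subjects. If all 8 men are fasted first, the fed/fasted ratio is the food effect multiplied by whatever differs between the two periods. The fed and fasted safety summaries share the problem.

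If the order is in fact random, the labels fail instead. Protocol 14.4.1 and SAP 9.1.9 equate Period 1 with fasted and Period 2 with fed, and SAP 9.1 summarises Part II by period. With a balanced allocation, 4 of 8 men would have their events and safety data under the wrong condition. Protocol 14.1 asks for summaries by fed or fasted, which is the same grouping only under a fixed order.

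The Part I safety objective is not affected.

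**Working it through.** **Inputs from the documents.** Eight men, each dosed twice (Protocol 4.1). Washout of at least 1 week or at least 5 half-lives, whichever is longer (Protocol 4.3). No power, alpha, CV or period effect is given (Protocol 14.2, SAP 3.1.1), so there is no planned figure to reproduce.

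**Step 1: can food and period be separated?** Write the model as 8 subject effects, one period effect and one fed effect: 10 columns and 16 observations.

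| Order | Rank | Correlation of period with fed |
|---|---|---|
| Fasted then fed for all 8 | 9 of 10 | 1.0 |
| 4 fasted-first, 4 fed-first | 10 of 10 | 0.0 |

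Under the fixed order the two effects are one column. With a true food ratio of 1.00, assumed period ratios of 0.80, 0.90, 1.10 and 1.25 come out as fed/fasted ratios of 0.80, 0.90, 1.10 and 1.25. Under 4+4 the estimate stays at 1.00 in each case.

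**Step 2: are the fixed labels compatible with randomization?** If each man were allocated 1:1 independently, the chance that all 8 are fasted first is 0.5^8 = 0.4%.

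**Step 3: what does a period effect do to the interval under the fixed order?** Assumptions: within-subject CV of 20% or 30%, log-normal data, paired analysis with 7 degrees of freedom.

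- SD of the log difference = √2 × √ln(1 + CV²) = 0.280 (CV 20%) or 0.415 (CV 30%).
- SE = SD/√8 = 0.0990 or 0.1468.
- 90% half-width = 1.895 × SE = 0.188 or 0.278, so the interval is the ratio × 0.829 to 1.206, or × 0.757 to 1.321.
- Coverage = P(|T| < 1.895), with T noncentral t on 7 df and noncentrality ln(period ratio)/SE. At a 10% period effect the noncentrality is 0.0953/0.0990 = 0.963 or 0.0953/0.1468 = 0.649.

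| Assumed period effect | Coverage of nominal 90% CI, CV 20% | CV 30% |
|---|---|---|
| 3% | 88.8% | 89.4% |
| 5% | 86.6% | 88.5% |
| 10% | 77.5% | 84.2% |
| 20% | 49.3% | 69.6% |

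A 5% effect is 0.26 (CV 20%) or 0.18 (CV 30%) of the half-width on the log scale; a 10% effect is 0.51 or 0.34. Simulation of 200,000 trials at 5%, 10% and 20% agrees within 0.2 points. A simulated 4+4 crossover with a period term and a 20% period effect gives coverage of 90.1% (CV 20%) and 89.9% (CV 30%).

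**Step 4: what does randomising cost in precision?** Width ratio against a paired analysis of the same n completers = t(0.95, n−2) × √[(1/n1 + 1/n2)/4] ÷ [t(0.95, n−1) × √(1/n)].

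| Completers per order | Width ratio |
|---|---|
| 4+4 | 1.026 |
| 4+3 | 1.048 |
| 3+3 | 1.058 |
| 4+2 | 1.122 |

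For 4+4: (1.943 × √0.125) ÷ (1.895 × √0.125) = 1.026.

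**Step 5: carryover.** Five half-lives leave 0.5^5 = 3.1% of the drug, and a Period 2 pre-dose sample is scheduled. Carryover is a minor concern, but a washout does not remove other differences between periods.

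**The case against.** The strongest reply is that 9.3 contains one mis-drafted clause. Every passage that states an order agrees on fasted first, Part II has no randomization row, and 9.3 itself speaks of the same order. A fixed sequence is then a design choice with a known limitation. That is probably the right reading of intent. But correcting the clause confirms the confounded design, and no visible passage acknowledges the limitation.

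It is also fair that the harm is hypothetical. Part II is unpowered and exploratory, nothing in the documents suggests a period effect of 10% or more, and the same men are dosed under controlled conditions after a long washout. This limits the weight of the point. It does not answer it, because a fixed order gives no means of checking.

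The mislabelling under a random order is narrower than it may look. SAP section 7 summarises Part II PK by condition, so only adverse event and safety outputs would be affected. The silence of SAP section 11 is weak evidence, since that section covers analyses and not dosing order.

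Some text is not visible: the Part II schedule footnotes on fed dosing and breakfast, most of SAP 3.4, and the food-effect section named in the SAP contents. A clarification of the order could sit there, and no claim is made about the planned model. No model could separate food from period under one order, and the conflicting sentences are all intact.

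Finally, a reason may exist for giving the fasted dose first, since Part I is entirely fasted. The visible text states none.

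**Conclusion.** The concern holds and should be fixed before Part II dosing. The contradiction is in the current text of both documents. The confounding under the fixed order is structural and needs no assumption. Its size is unknown: on the assumed CVs of 20% and 30%, the harm is small for a period effect of 5% or less and material at 10% or more, and the fixed-order design cannot show which applies. It bears on one secondary objective and on the fed versus fasted safety comparison.

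**What to change.** State which order is intended and make all passages agree.

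**Preferred: randomise.** Allocate the 8 men 4:4 to fasted-fed or fed-fasted. Include sequence, period, condition and subject terms in the food-effect model. Define and summarise Part II adverse events and safety data by condition, not by period. This needs a list of 8 sequence assignments and amendments to Protocol 5.4, 9.1.3 (which does not describe a Part II allocation), 14.4.1 and Appendices 2, 4 and 5. In the SAP it touches 3.2, 3.5 (its rule for replacing men randomized but not dosed covers Part I only), 6.6, 9.1, 9.1.1, 9.1.9 and the Part II schedule. No extra subjects or visits are needed. The interval is 2.6% wider with 4+4 completers. Dosed dropouts are not replaced, so the loss can reach 4.8% with 4+3, 5.8% with 3+3 or 12.2% with 4+2.

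**If fasted first is intended.** Remove the random assignment from 9.3, and state in the protocol, SAP and study report that the fed/fasted ratio is confounded with period. The cost is a wording change and a declared limitation.

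**In either case**, reword the two-arms phrase in 9.3 as 8 subjects in total, each receiving both conditions.

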## 9.4 Accountability

The Investigator is responsible for ensuring that all drug substance and study drug is inventoried, accounted for and documented in accurate accountability records. Upon completion of the study and/or as requested by Indivior, copies of study drug and drug substance accountability records will be provided to Indivior. After the monitor completes reconciliation, all unused study drug will be destroyed by the Investigator, as per local standard operating procedures (SOP), after Indivior has approved the commencement of destruction. All unused drug substance and requested retain samples will be maintained at appropriate storage conditions and shipped according to the details in the Pharmacy Manual. The IMP must be handled strictly in accordance with the protocol, handling guidelines and the label; it must be stored in a locked, limited-access area under appropriate environmental conditions.

Subject level dispensation of IMP must be documented on the appropriate subject level accountability form. All IMP dispensation will be performed by a pharmacist or designee, checked by a study site staff member and documented on a drug dispensation form.

Used IMP bottles (for both powder in solution and capsule), and unused IMP must be available for verification by the site monitor during monitoring visits.

## 9.5 Reporting Product Complaints

The Investigator and study site staff are responsible for prompt reporting of product quality complaints to Indivior. A product complaint is any concern pertaining to the preparation or quality of the drug substance or IMP, and includes, but is not limited to, broken capsules, labelling defects or packaging defects, IMP that is thought to be ineffective, or has an appearance, taste or odour that is outside of what is expected.

All product complaints should be reported to Indivior manner and the following information provided: in a timely

- study number
- site contact/reported by
- subject number (if already assigned to a subject)
- description of issue
- picture, if available (photographs should be taken only if safe to do so/within site policy or practice to take photograph)

Retain the product and packaging in quarantine for further investigation, as required.

#### 9.6 Concomitant Therapies

Concomitant therapies (medications) will be collected from screening until the EOS visit or the ET visit, and at the time points listed Section 22.1, Appendix 1 and Section 22.2, Appendix 2. Any concomitant medications (including herbal preparations) taken during the study will be recorded in the source documents and in the eCRF. Any changes in concomitant therapy during the study will be documented, including cessation of therapy, initiation of therapy and dose changes.

Any changes to concomitant therapies that are not listed as permitted concomitant therapies should be discussed with the study Medical Monitor.

